CMV	Cytomegalovirus
CNV	Choroidal Neovascularization
CNTF	Ciliary Neurotrophic Factor
CoA	Certificate of Analysis
CRA	Clinical Research Associate
CRF	Case Report Form
CRP	C-Reactive Protein
CT	Computed Tomography
CTCAE	Common Terminology Criteria for Adverse Events
DLT	Dose-Limiting Toxicity
DSMB	Data Safety Monitoring Board
EC	Ethics Committee
ESR	Erythrocyte Sedimentation Rate
EBs	Embryoid Bodies
EBV	Epstein–Barr Virus
ECG	Electrocardiogram
ERG	Electroretinography
ETDRS	Early Treatment Diabetic Retinopathy Study

Abbreviation	Definition
FA	Fluorescein Angiography
FAF	Fundus Autofluorescence (imaging)
fCNV	Foveal Choroidal Neovascularization
FGF	Fibroblast Growth Factors
FRI	Functional Reading Independence (FRI) Index
G	Gauge (Needle wire gauge)
GA	Geographic Atrophy
GCP	Good Clinical Practice
GGT	Gamma Glutamyl Transferase
GMP	Good Manufacturing Practice
GTT	Guttae (Drops)
Gr	Gram
HBsAg	Hepatitis B Surface Antigen
HCVAb	Hepatitis C Virus Antibody
H&E	Hematoxylin and Eosin stain
HBV	Hepatitis B Virus
HCV	Hepatitis C Virus
hESCs	Human Embryonic Stem Cells
HLA	Human Leukocyte Antigen(s)
HIV	Human Immunodeficiency Virus
IB	Investigator's Brochure
IFU	Instructions for Use
IgM	Immunoglobulin M
INR	International Normalized Ratio (of prothrombin time of blood coagulation)
IOP	Intraocular Pressure
iPSCs	Induced Pluripotent Stem Cells
IR	Infrared
IRB	Institutional Review Board
IRF	Intraretinal Fluid
LDH	Lactic Dehydrogenase

Abbreviation	Definition
MEF	Mouse Feeder Cells
MITF	Microphthalmia-associated Transcription Factor
mL	Milliliter
MM	Medical Monitor
mm	Millimeter
MTD	Maximally Tolerated Dose
NCI	National Cancer Institute
NEI VFQ-25	National Eye Institute Visual Function Questionnaire-25
ng	Nanogram
OCT	Ocular Coherence Tomography
OD	Oculus Dexter (the right eye)
OKR	Optokinetic Reflex
OS	Oculus Sinister (the left eye)
OU	Oculus Utergue (both eyes)
PD	Project Director
PED	Pigment epithelial detachment
PEDF	Pigment Epithelium-Derived Factor
PMEL17	Premelanosome protein
PO	Per Os (by mouth)
POS	Photoreceptor Outer Segments
PSA	Prostate Specific Antigen
PT	Prothrombin Time
PTT	Partial Thromboplastin Time
PVR	Proliferative Vitreo-Retinopathy
QC	Quality Control
QoL	Quality of Life
qPCR	quantitative Polymerase Chain Reaction

Approval of Clinical Research Protocol No. CCN_CT02 – Amendment #14

1. STUDY SYNOPSIS

Protocol Number

CCN_CT02

Protocol Title

Phase I/IIa Dose Escalation Safety and Efficacy Study of Human Embryonic Stem Cell-Derived Retinal Pigment Epithelium Cells Transplanted Subretinally in Patients with Advanced Dry-Form Age-Related Macular Degeneration (Geographic Atrophy)

Sponsor

Cell Cure Neurosciences Ltd./BioTime, Inc.

Study Centers and Planned Geographical Distribution

Multicenter multinational trial

Clinical Phase

Phase I/IIa study

Investigational Product

OpRegen® is a cell-based product composed of retinal pigment epithelium (RPE) cells, derived from human embryonic stem cells (hESCs) through a process of directed differentiation. OpRegen® can be implanted as a single cell suspension to form a targeted suspension of 50×10^3 to 200×10^3 in a total volume of 50-100 μL in either an ophthalmic

Study Duration

- Screening period of up to [REDACTED].
- Part 1: Eligible subjects will be enrolled into Part 1 of the trial for approximately 52 weeks (up to ± 14 days) for a post-implantation follow up assessment.
- Part 2: Following the successful completion of Part 1 of the study, subjects will continue into Part 2 defined as the long term follow up with evaluations at [REDACTED], [REDACTED].

Study Objectives

Primary Objectives

To evaluate the safety and tolerability of human embryonic stem cell-derived retinal pigment epithelium cells (OpRegen®), transplanted subretinally to subjects with advanced dry age-related macular degeneration (AMD) with geographic atrophy (GA).

Secondary Objectives

To evaluate the preliminary efficacy of OpRegen® treatment by assessing the changes in ophthalmological parameters as measured by various methods of primary clinical relevance.

¹ Refer to Section 2.3 in the Investigator Brochure for more information about the Product Description

[REDACTED]

Study Endpoints

Safety and Tolerability Endpoints

Safety and tolerability of OpRegen® treatment will be assessed by:

- Incidence and frequency of treatment emergent adverse events (AEs)
- Treatment emergent changes in the following variables:
 - Vital signs
 - Hematology/ Blood Chemistry/ Urinalysis
 - Physical examination
 - Ophthalmological evaluations including:
 - ✓ Best Corrected Visual Acuity (BCVA)
 - ✓ Dilated Fundus Exam
 - ✓ Intraocular Pressure (IOP)
 - ✓ Slit Lamp Examination (SLE)
 - ✓ Spectral Domain Optical Coherence Tomography (SD-OCT)
 - ✓ Fluorescein Angiography (FA)
 - ✓ Microperimetry
 - ✓ Fundus Autofluorescence (FAF)
 - ✓ Color Fundus Photography (CFP)

[REDACTED]

Efficacy Endpoints of Clinical Relevance

Preliminary efficacy assessments will utilize the below listed parameters:

- Directional change in the geographic atrophy (GA) lesion area over time
- Overall change in the GA lesion area of the study eye over time using SD-OCT and FAF
- Change from baseline over time in BCVA as measured by Early Treatment Diabetic Retinopathy Study (ETDRS) chart
- Change from initial assessment over time in retinal sensitivity (as assessed by microperimetry)
- Change from baseline over time in Reading Speed Test
- Change from baseline over time in Low Luminance BCVA
- Correlation assessment between quantitative metrics derived from FAF, SD-OCT and CFP images
- Correlation assessment between functional and structural changes
- Change over time in National Eye Institute Visual Function Questionnaire-25 (NEI VFQ-25) Quality of Life (QoL) score
- Change over time in Functional Reading Independence (FRI) Index score

Study Hypothesis

Implantation of OpRegen® to subjects with advanced dry-form AMD with GA is safe, well-tolerated and provides preliminary efficacy evidence.

Study Design

Open-label, dose escalation study of approximately 24 subjects with advanced dry-AMD and GA divided into cohorts:

Cohorts 1 – 3

The first 2 cohorts, each consisting of 3 eyes of 3 legally blind subjects with best corrected visual acuity of 20/200 or less in the study eye, will receive a single subretinal implantation of OpRegen®.

The third cohort will include up to 6 eyes of 6 subjects with best corrected visual acuity of 20/200 or less in the study eye, who will receive a single subretinal implantation of OpRegen®.

Staggered intervals within and between cohorts will be applied to ensure subjects safety and welfare.

Cohort 4

The fourth cohort will include approximately 12 eyes from 12 subjects with BCVA between 20/64 and 20/250 in the study eye, who will receive a single subretinal targeted implantation of OpRegen®.

Cohort 4 will include two formulations; subjects will be treated with either OpRegen® BSS Plus or OpRegen® ‘Thaw-and-Inject’ (TAI) formulation, which is based on the use of CryoStor® 5, a serum-free, animal-free GMP grade cryopreservation solution. Additionally, this Cohort includes two options for subretinal delivery systems: DORC² or the Orbit SDS (an FDA 510K class II device cleared under K182274 on 20 November 2018). Please refer to the instructions for use (IFU) for each device for more information.

Staggered intervals will be applied between at least the first two subjects of each delivery modality to ensure subject safety and welfare.

[REDACTED]

[REDACTED]

All Cohorts

The study is being conducted in participants with confirmed bilateral GA (Study Eye and Non-Study, Fellow Eye).

Between cohorts and subjects, where applicable, the next step to proceed will be per Data Safety Monitoring Board (DSMB) recommendation, based on accumulated safety data.

Cell suspension will be delivered into the subretinal space in the macular area as described in the IFU and operating manuals for each delivery device.

[REDACTED]

[REDACTED]

[REDACTED]

[REDACTED]

[REDACTED]

Along with the relevant surgical procedure, subjects will receive systemic immunosuppression [REDACTED], consisting of the following:

- [REDACTED]
- Systemic (PO) tacrolimus 0.01 mg/kg daily [REDACTED] up to 6 weeks post transplantation,
- Systemic (PO) mycophenolate mofetil, up to 2 gr/day, [REDACTED] for at least three months [REDACTED] post transplantation, [REDACTED]

During Part 1 of the study, subjects will be assessed at pre-scheduled intervals throughout the [REDACTED] following the implantation of OpRegen®. Any side effects related to the immunosuppressive treatment will be monitored and followed up (e.g. improve blood pressure control if hypertension develops). In the case of uncontrollable side effects, treatment with the immunosuppressive agents described above will be modified in consultation with the Medical Monitor.

Part 2 of the study includes long term follow-up visits that will occur at [REDACTED]

Study Population and Number of Subjects

The study will enroll a total of approximately 24 subjects, 50 years and older with non-neovascular (dry) age-related macular degeneration (AMD), who have funduscopy findings of geographic atrophy in the macula, BCVA of 20/200 or less (legally blind) in cohorts 1-3, and between 20/64 and 20/250 in cohort 4 in the (worse) study eye and the absence of additional concomitant ocular disorders.

Inclusion/Exclusion Criteria for Cohorts 1 – 3

Inclusion Criteria

1. Age 50 and older.
2. Diagnosis of dry- (non-neovascular) AMD in both eyes.
3. Funduscopy findings of dry-AMD with progressive geographic atrophy in the macula, [REDACTED]

4. Best corrected central visual acuity equal or less than 20/200 in the study eye by ETDRS vision testing.
5. Vision in the non-operated eye must be better than or equal to that in the operated eye.
6. Subjects with sufficient good health that can participate in all study-related procedures and complete the study follow-up period (based on medical records).
7. Ability to undergo a vitreoretinal surgical procedure under monitored anesthesia care.
8. Blood counts, blood chemistry, coagulation and urinalysis without abnormal significance.
9. Negative for HIV, HBC, and HCV. Negative for CMV IgM and EBV IgM.
10. Willing to defer donation of blood and tissues.
11. Able to understand study procedures and willing to sign informed consent.

Exclusion Criteria:

1. Evidence of neovascular AMD by history, as well as by clinical exam, fluorescein angiography (FA), or ocular coherence tomography (OCT) at baseline in either eye.
2. History or presence of diabetic retinopathy, vascular occlusions, uveitis, Coat's disease, uncontrolled glaucoma, cataract or media opacity preventing posterior pole visualization or any significant ocular disease other than AMD that has compromised or could compromise vision in the study eye and confound analysis of the primary outcome.
3. History of retinal detachment repair in the study eye.
4. Axial myopia greater than -6 diopters.
5. At least 2 months following cataract removal in the study eye and Yttrium Aluminum Garnet (YAG) laser capsulotomy in the study eye in the past 4 weeks and any other ocular surgery in the study eye in the past 3 months prior to OpRegen® implantation.
6. History of cognitive impairment or dementia.
7. Contraindication for systemic immunosuppression.
8. History of any condition other than AMD associated with choroidal neovascularization in the study eye (e.g. pathologic myopia or presumed ocular histoplasmosis).
9. Any type of systemic disease or its treatment, in the opinion of the Investigator, including any medical condition (controlled or uncontrolled) that could be expected to progress, recur, or change to such an extent that it may bias the assessment of the clinical status of the patient to a significant degree or put the patient at special risk.
10. For female subjects; pregnancy or breastfeeding.
11. Current participation in another clinical study. Past participation (within 6 months) in any clinical study of a drug administered systemically or to the eye.
12. Currently receiving aspirin, aspirin-containing products and/or any other coagulation modifying drugs which cannot be discontinued 7 days prior to surgery
13. History of cancer (other than a non-melanoma skin cancer). For cancers in remission for more than five years, enrollment is allowed with concurred documented approval of principal investigator and oncologist prior to enrollment.³

Note: "Live" attenuated vaccination prohibited during active systemic immunosuppression.

³ In the case of any suspected malignancies at screening, patient should be referred to appropriate medical specialist.

Inclusion/Exclusion Criteria for Cohort 4

Inclusion Criteria

1. Age 50 and older.
2. Diagnosis of dry- (non-neovascular) AMD in both eyes.

[REDACTED]

11. BCVA letter score of ≥ 29 letters and ≤ 64 letters (Snellen equivalent of 20/64 – 20/250) in treated eye using ETDRS charts at starting distance of 4m.
12. Visual acuity as measured by ETDRS in the non-operated eye must be better than or equal to that in the operated eye.
13. Subjects with sufficient good health that can participate in all study-related procedures and complete the study follow-up period (based on medical records).
14. Ability to undergo a vitreoretinal surgical procedure under monitored anesthesia care.
15. Blood counts, blood chemistry, coagulation and urinalysis without abnormal significance.
16. Negative for TB, HIV, HBC, and HCV. Negative for acute or reactivated CMV IgM and EBV IgM or asymptomatic in the opinion of the investigator.
17. Willing to defer donation of blood and tissues.
18. Able to understand study procedures and willing to sign informed consent.

Exclusion Criteria:

1. Evidence of neovascular AMD by history, as well as by clinical exam, fluorescein angiography (FA) at ocular coherence tomography (OCT) at baseline in either eye.

[REDACTED]

[REDACTED]

8. At least 2 months following cataract removal in the study eye and Yttrium Aluminum Garnet (YAG) laser capsulotomy for both eyes. Any other ocular surgery in either eye in the past 3 months prior to OpRegen® implantation.
9. Current participation in another clinical study of an active drug (placebo and sham will be allowed). Past participation (within 6 months) in any clinical study of a drug administered systemically (except for vitamins and minerals) or to the eye.
10. History of cognitive impairment or dementia
11. Contraindication for systemic immunosuppression
12. Any type of systemic disease or its treatment, in the opinion of the Investigator, including any medical condition (controlled or uncontrolled) that could be expected to

progress, recur, or change to such an extent that it may bias the assessment of the clinical status of the patient to a significant degree or put the patient at special risk.

13. For female subjects; pregnancy or breastfeeding
14. Currently receiving aspirin, aspirin-containing products and/or any other coagulation modifying drugs which cannot be discontinued 7 days prior to surgery
15. History of cancer (other than a non-melanoma skin cancer). For cancers in remission for more than five years, enrollment is allowed with concurred documented approval of principal investigator and oncologist prior to enrollment.⁴
16. Known allergy to any of the study medications or formulations
17. Inability to comply with study or follow-up procedures
18. Inability to obtain CFP, FAF, OCT/OCTA and microperimetry of sufficient quality to be analyzed and graded by the Central Reading Center

Note: "Live" attenuated vaccination prohibited during active systemic immunosuppression.

Final decision for subject eligibility upon confirmation of Central Reading Center and the Sponsor.

Statistical Considerations

As this is an open label, phase I/IIa dose escalation, safety, tolerability and preliminary efficacy study, neither power assessment, nor formal hypotheses testing are currently planned for study outcome measures.

The planned sample size of approximately 24 treated eyes, [REDACTED], with targeted doses of 50×10^3 and up to 200×10^3 cells, is considered clinically appropriate for further characterization of the safety, tolerability and preliminary efficacy of OpRegen in the treatment of subjects with advanced dry-form AMD with GA.

Comprehensive interim reports of accumulated safety, tolerability and preliminary available efficacy data will be presented to the independent Data Safety Monitoring Board (DSMB) prior to escalation to the next to come study dose and to enrolment of the next to come study cohort. Between cohorts, and subjects if applicable, the next step to proceed will occur per DSMB recommendation, based on accumulated safety data.

All measured variables and derived parameters will be listed individually and if appropriate, presented in summary tables by dose regimen group and overall, providing sample size, absolute and relative frequency for categorical variables, or sample size, arithmetic mean, standard deviation, median, minimum and maximum for continuous variables. Confidence intervals will be presented for the efficacy endpoints for exploratory purposes only. Complete analyses to be prospectively performed will be outlined in a separate statistical analysis plan (SAP).

⁴ In the case of any suspected malignancies at screening, patient should be referred to appropriate medical specialist.

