22. STATISTICAL METHODOLOGY

22.1 STUDY DESIGN AND SAMPLE SIZE

As this is an open-label, phase I/IIa dose escalation, safety, tolerability and preliminary efficacy study, neither power assessment, nor formal hypotheses testing are currently planned for study outcome measures.

Detailed methodology for data summary and analyses will be documented in a Statistical Analysis Plan (SAP). This document may modify the plans outlined in the protocol; however, any major modification of the outcome measures and/or its analysis will also be reflected in a protocol amendment. Additional statistical analyses other than those described in this section may be performed if deemed appropriate and included in the SAP.

The planned sample size of approximately 24 eyes for 4 study cohorts to be treated with targeted OpRegen® doses of 50×10^3 and up to 200×10^3 cells, is considered clinically appropriate for further characterization of the safety, tolerability and preliminary efficacy of OpRegen® in the treatment of subjects with subjects with advanced dry-form AMD with GA.

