## VERSION HISTORY

Version	Date	Status/Reason for Changes
1.0	12 October 2022	Initial Draft

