### Purpose of the Statistical Analysis Plan (SAP)

The purpose of this document is to provide a description of the statistical methods and procedures to be implemented for the analysis of data from the OpRegen clinical trial CCN-CT02. This document is based on protocol version amendment number 14, dated 9 April 2019. Any revisions to the SAP (both alternative and additional methods) will be made prior to database lock(s) and reasons for such revisions will be described in the final Clinical Study Reports ([CSR](#)).

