### 3.3 Study Hypothesis

As this is an open label, phase I/IIa dose escalation, safety, tolerability, and preliminary efficacy study, neither power assessment, nor formal hypotheses testing were planned for study outcome measures. However, for purposes of data analyses and this SAP, the Sponsor hypothesizes that implantation of OpRegen to subjects with advanced dry-form AMD with GA is safe, well-tolerated and provides evidence of preliminary efficacy based on pre-specified functional and structural assessments.

The primary hypothesis is that there will be no dose-limiting toxicity (DLT) and that implantation of OpRegen to subjects with progressive dry-form AMD with GA will be safe and well-tolerated. For this study DLT is defined as an SAE determined to be product related.

A secondary null hypothesis is that there will be no difference in disease progression, as measured by retinal function and structure, between the treated and untreated regions in the treated eye and between the treated and untreated eye of a subject.

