#### 4.0 STUDY DESIGN

Open-label, dose escalation study of 24 subjects with advanced dry-[AMD](#) and [GA](#) divided into four cohorts ([Figure 1](#)):

##### Cohorts 1 – 3

The first 2 cohorts, consisted of 3 eyes of 3 legally blind subjects with best corrected visual acuity of 20/200 or less in the study eye, all received a single subretinal implantation of OpRegen.

The third cohort included 6 eyes of 6 subjects with best corrected visual acuity of 20/200 or less in the study eye, all received a single subretinal implantation of OpRegen.

Staggered intervals and safety data review by the independent data safety monitoring board ([DSMB](#)) occurred within and between cohorts to ensure subjects safety and welfare.

##### Cohort 4

The fourth cohort included 12 eyes from 12 subjects with [BCVA](#) between 20/64 and 20/250 in the study eye, all received a single subretinal targeted implantation of OpRegen.

Staggered intervals and safety data review by the [DSMB](#) occurred between at least the first two subjects of each delivery modality to ensure subject safety and welfare.

[figure not shown]

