## 6.0 STATISTICAL ANALYSIS GENERAL CONSIDERATIONS

The planned sample size of 24 treated eyes, [REDACTED], with targeted doses of  $50 \times 10^3$  and up to  $200 \times 10^5$  cells, is considered clinically appropriate for further characterization of the safety, tolerability, and preliminary efficacy of OpRegen in the treatment of subjects with advanced dry-form [AMD](#) with [GA](#).

Comprehensive interim reports of accumulated safety, tolerability and preliminary available efficacy data were presented to the [DSMB](#) prior to escalation to the next to come study dose and to enrolment of the next to come study cohort. Between cohorts, and subjects when applicable, the next step to proceed occurred per [DSMB](#) recommendation based on accumulated safety data.

All measured variables and derived parameters will be listed individually and if appropriate, presented in summary tables by dose regimen group and overall, providing sample size, absolute and relative frequency for categorical variables, or sample size, arithmetic mean, standard deviation, median, minimum, and maximum for continuous variables. [Confidence intervals](#) will be presented for the efficacy endpoints for exploratory purposes only. Complete analyses to be prospectively performed are outlined in this SAP.

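### SAP 6.0 calls its analyses prospective, but the SAP was first drafted in October 2022, after all 24 subjects had been dosed open-label; its departures from Protocol Amendment 14 should be labelled as such and the omitted protocol summaries restored

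*Protocol*

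**What the plan says.** The synopsis (Statistical Considerations) makes a forward promise: "Complete analyses to be prospectively performed will be outlined in a separate statistical analysis plan (SAP"). SAP 6.0 takes it up in the present tense: "Complete analyses to be prospectively performed are outlined in this SAP". SAP 3.3 frames the sponsor's hypothesis as "evidence of preliminary efficacy based on pre-specified functional and structural assessments".

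On timing, the SAP version history has one entry, 1.0, an initial draft dated "12 October 2022". SAP 2.0 names its basis: "This document is based on protocol version amendment number 14, dated 9 April 2019". SAP 4.0 describes the trial as an "Open-label, dose escalation study of 24 subjects with advanced dry" AMD and reports each cohort in the past tense; of Cohort 4 it says "all received a single subretinal targeted implantation of OpRegen". SAP 6.0 adds that interim reports containing preliminary efficacy data had already been presented to the DSMB. Protocol 20.2 explains why the sponsor is not blinded to the data it supplies to that board.

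On changes, Protocol 22.1 allows the SAP to modify the protocol's plans, with the condition that "any major modification of the outcome measures and/or its analysis will also be reflected in a protocol amendment".

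**The concern.** An analysis plan is prospective in a useful sense if its choices were made before anyone choosing could see the outcomes. Here the first draft postdates dosing of the last subject, the design is open-label, and the sponsor had the data it passed to the DSMB. Choices that appear for the first time in this SAP therefore cannot be assumed independent of the results, yet SAP 6.0 gives them the same label as content fixed in the protocol.

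What is at stake is the reading of the efficacy section of the clinical study report. If the endpoints that get a table are a subset settled in October 2022, and the report calls the analyses prospective, a reader cannot separate protocol-defined results from later choices, and cannot see what the endpoints left out would have shown.

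**Working it through.** **Chronology**

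- Cohort sizes in SAP 4.0, with 3 subjects in each of Cohorts 1 and 2: 3 + 3 + 6 + 12 = 24. This reproduces the SAP's stated total, so the past-tense account covers every subject.
- From Amendment 14 (9 April 2019) to SAP 1.0 (12 October 2022): 1,096 days to 9 April 2022 plus 186 days to 12 October = 1,282 days, and 1,282 / 365.25 = 3.51 years. The SAP cites no later amendment.

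**What keeps its pre-specified status**

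The ten efficacy endpoints in SAP 3.2.4 are the ten in Protocol 7.3.4. The exploratory two-sided 0.05 level (Protocol 22.3, SAP 6.2) and the examination of the untreated eye (Protocol 22.14, SAP 7.0) are also carried over.

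**What the SAP changes**

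| Topic | Protocol Amendment 14 | SAP 1.0 |
|---|---|---|
| Efficacy endpoints analysed | Ten (7.3.4, 22.12.1) | Four of the ten itemised in 7.1.10: directional GA change, GA area, BCVA, low-luminance BCVA |
| Microperimetry, reading speed, two correlation assessments, NEI VFQ-25, FRI | Listed as efficacy endpoints | Not itemised in 7.1.10; no table, figure or listing named in Section 11 |
| GA area modality | SD-OCT and FAF | FAF only in 7.1.10, although 3.2.4 still names both |
| IOP | Safety evaluation (7.3.1) | Kept under safety in 3.2.1, and added to the efficacy analyses (7.1.10) and efficacy outputs (Section 11) |
| GA annual rate | Not in the 7.3.4 list; rate of progression is mentioned in 6.3 and 14.2 | Separate figure and listing in Section 11 |
| Missing data | Last observed value, when appropriate (22.6) | No imputation apart from dates, unless otherwise noted (6.3) |

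Count: 10 − 4 = 6 protocol endpoints without an itemised analysis or a named output. One of the four retained is narrowed to a single modality. Two analyses or outputs are added, and one missing-data rule is replaced.

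Section 11 matters because SAP 7.0 says data will be presented as that section indicates. Its efficacy outputs are confined to GA, GA annual rate, BCVA and IOP. Low-luminance BCVA has no output of its own and may be meant to sit within the BCVA outputs. The GA table title names no modality, so it does not settle whether SD-OCT is included.

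**The case against.** Several points on the other side are sound.

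- The synopsis sentence is only a promise that a SAP will follow, and nothing in it is wrong. The statement that conflicts with the timing is the one in SAP 6.0.
- A reader might infer that SAP 3.3 misuses the word pre-specified. It does not: the word there describes the assessments, and those were in the protocol.
- A reader might infer that endpoints were picked because of their results. The documents do not show this. The reporting they record was to the DSMB, before dose escalation and before each next cohort. They do not show that efficacy results from Cohort 4, the cohort Protocol 6.2 designates for efficacy exploration, had been reported.
- SAP 2.0 places revisions before database lock. That is some discipline, but lock protects only if results are unseen until then.
- Protocol 22.1 lets the SAP change plans and add analyses; only major changes need an amendment. A breach cannot simply be asserted.
- SAP 7.1.10 says all efficacy data will be listed and refers to summaries for all variables, and SAP 6.4 says much the same. This softens the omission. It does not remove it, since the itemised list and Section 11 are what will be programmed.
- Some omitted tests applied to few subjects: microperimetry was optional in Cohort 3, reading speed was mandatory only for English speakers, and FRI did not apply to Cohorts 1–3. That does not explain the selection, because low-luminance BCVA carries a similar restriction and was kept, while NEI VFQ-25 has none in Table 1 and was left out.

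It is also tempting to attach a false-positive rate for ten endpoints at 0.05. That would measure multiplicity already present in Amendment 14, which had the same endpoints and level, and not any effect of choosing late. No formal testing is planned and confidence intervals are exploratory, so no error rate is offered here.

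**Conclusion.** The point holds in a limited form. SAP 6.0 overstates the status of what the SAP itself introduced. The ten endpoints and whatever else comes from Amendment 14 remain pre-specified. The departures tabulated above were first set down when open-label outcome data could have been seen, and should be read as such. The annual-rate output is the mildest of these, since the protocol text anticipates a rate of progression. Replacing last observed value may well be defensible on its merits; the issue is its dating and disclosure.

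The size is six of ten protocol efficacy endpoints without an itemised analysis or named output, one endpoint narrowed, two additions and one missing-data change. No stated figure changes, and in a descriptive 24-subject study no dosing or sample-size decision turns on it. The effect is on what the study report may claim.

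Two assumptions carry this. Completion of dosing rests on the SAP's past tense, because no dosing dates are visible. Data access by those writing the SAP is inferred from the open-label design and Protocol 20.2; it is possible, not documented.

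**What to change.** 1. In SAP 7.1.10 and Section 11, restore descriptive summaries for all ten Amendment 14 efficacy endpoints, with GA area by SD-OCT as well as FAF and with low-luminance BCVA named. Report these first.
2. In SAP 6.0, limit the word prospectively to Amendment 14 content. Add a short dated table of every SAP departure, including the missing-data change, labelled as chosen after open-label data were available. Call SAP-only analyses post hoc in the study report. SAP 3.3 can stand.
3. For each departure, state whether it is major under Protocol 22.1 and so needs a protocol amendment, with a one-line reason.

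SAP 2.0 already allows revision before database lock, with reasons given in the study report, so the route exists. No new data or visits are needed. The cost is a few extra tables, some for tests done in only part of the sample, and an efficacy statement slightly weaker than the present wording would allow.
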